2.5.3 Per-Protocol Population #2 (PP2)

A second Per-Protocol population (PP2) will include all subjects in the ITT population who do not have major protocol deviations or clinically important intercurrent events thought to confound assessment of primary outcomes. The PP2 population will be provided for primary and secondary efficacy endpoints.

2.5.4 Safety Population (SP)

The Safety Population (SP) will consist of ITT subjects who receive at least 1 dose of study medication (Camostat mesilate or placebo). Subjects will be analyzed according to the study treatment received. The Safety population will be used for all summaries of safety and tolerability data.

2.6 BLINDING

This is randomized, double-blind, placebo-controlled study. Subjects will be randomized in a 2:1 ratio to Camostat mesilate:placebo. None of the investigators, study site personnel, Sponsor, or subjects will know to which treatment the subjects were randomized. Additional details of the blinding are provided in the Clinical Study Protocol (NI03-CV19-001 Version 4.0).

3 DESCRIPTION OF OUTCOME MEASURES

This section provides definitions of specific variables and concepts relevant to this Statistical Analysis Plan for primary and second efficacy outcomes. Please refer to the Clinical Trial Protocol for additional details.

3.1 PRIMARY ANALYSIS

Disease Progression (Hospitalization): The Primary Efficacy Endpoint is defined as status changing from ambulatory care to COVID-19 related hospitalization, ER visit, or death due to any cause on or prior to Day 28. Presenting to the emergency room is considered hospitalization. Hospitalization/ER visit and Death are recorded on the End of Study (EOS) form and will support the primary endpoint analysis. All subjects who have an End of Study form with any Hospitalization/ER Visit or Death are assumed to be COVID-related and therefore analyzed as a failure of the primary endpoint. Subjects failing the primary endpoint will be described within the Clinical Study Report.

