13.1 Determination of Sample Size

Assuming that the proportions of outpatients who are hospitalized for COVID-19 related disease or die due to any reason within 28 days of randomization are 30% and 15% for placebo and camostat mesilate groups, respectively, based on the two-sided Fisher's Exact Test, at the target significance level of 5%, 275 outpatients (183 in camostat mesilate group and 92 in placebo group) are needed to achieve 80% power. Thus, approximately 300 outpatients (200 in the camostat mesilate group and 100 in the placebo group) will be randomized to account for subject drop-out.

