2.2 PRIMARY ENDPOINT

Proportion of subjects requiring COVID-19 related hospitalization (including emergency room visit) or who die due to any cause within 28 days of randomization.

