4.1.3 Testing of Primary Efficacy Hypothesis

Primary results will include the numbers and percentages of subjects in each treatment group requiring COVID-19 related hospitalization/ER visit or who died due to any cause within 28 days of randomization.

As noted in the next section, the study is statistically powered by assuming that $\pi_{cm} = 0.15$ and $\pi_{pl} = 0.30$ and the number of subjects to be randomized are 186 and 93, in the active and placebo arms, respectively. Consequently, the expected number of subjects to experience the event is nearly 28 for both arms, with 158 and 65 subjects in the active and placebo arms, respectively, not expected to experience the primary endpoint. Therefore, an unadjusted chi-squared test (or exact test, if expected cell counts are < 5 in either group) will be used to test the primary efficacy hypotheses using a two-sided type 1 error of 0.05. Superiority will be concluded if $p < 0.05$ and the proportion of subjects experiencing the event is smaller among subjects randomized to the active treatment. This is tantamount to specifying a one-sided type 1 error rate of $\alpha = 0.025$.

In addition to determining the p-value for the primary efficacy hypothesis, results will also be expressed in terms of a two-sided normal based (asymptomatic) 95% confidence interval estimating the treatment group difference in 28-day COVID hospitalization or death. The upper bound of the confidence interval will be interpreted as the smallest treatment effect consistent with the study results.

If the expected number of events in either group is less than five (5), a Fisher's exact test and exact binomial intervals will be provided.

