4.1.4 Sample Size Determination for the Primary Efficacy Hypothesis

Sample size determination assumed event rates of 15% and 30% in the active and placebo groups, respectively, 2:1 randomization, and a two-sided type 1 error rate of $\alpha=0.05$. Under these assumptions, an adjusted chi-square test will have 80% power for sample sizes of 186 and 93 in the investigational and placebo arms, respectively (total sample size = 279). The sample size is increased by approximately 7.5% to allow for up to 200 and 100, respectively, to account for loss-to-follow-up.

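### SAP 3.1 counts every hospitalization or ER visit as COVID-related, so the primary test is of an all-cause endpoint labelled COVID-19 related, and no planned analysis estimates the endpoint as stated

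*SAP*

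**What the plan says.** SAP 2.2 gives the primary endpoint as "Proportion of subjects requiring COVID-19 related hospitalization (including emergency room visit) or who die due to any cause within 28 days of randomization". Protocol 6.2.1 has the same definition. The qualifier COVID-19 related attaches to the hospitalization or ER visit; death counts whatever its cause. SAP 4.1.1, 4.1.2 and 4.1.3 repeat the qualifier in the analysis, hypothesis and testing sections, and so does the title of shell Table 14.2.1.1.

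SAP 3.1 opens with the same definition and then sets the rule that decides who is an event. Subjects whose End of Study form shows them "with any Hospitalization/ER Visit or Death are assumed to be COVID-related and therefore analyzed as a failure of the primary endpoint". It adds that they will be described in the study report.

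The sizing assumption is tied to the stated endpoint. The wording in Protocol 13.1 is: "proportions of outpatients who are hospitalized for COVID-19 related disease or die due to any reason within 28 days of randomization are 30% and 15" (per cent; placebo first, then camostat). SAP 4.1.4 carries the rates over without the qualifier: "Sample size determination assumed event rates of 15% and 30% in the active and placebo groups".

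SAP 1 states that the SAP prevails over the protocol where they differ, and Protocol 13 agrees. The rule in SAP 3.1 would therefore govern the primary test.

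**The concern.** Two different endpoints carry one name. By definition, an ER visit for an unrelated injury or a planned admission is not an event. Under the counting rule it is. Such visits are plausible here: Protocol 8.1 requires at least one risk factor (age 65 or older, or a listed chronic condition), and merely presenting to an emergency room counts.

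Two things are at stake. The first is labelling: the result would be presented as COVID-19 related hospitalization or death when it measures all-cause hospitalization, ER visit or death. The second is the effect being estimated. Unrelated events that the drug cannot prevent pull the relative risk towards 1 and lower power below what the 30%/15% assumption implies.

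**Working it through.** **Is the stated endpoint recovered anywhere?** The rows of shell Table 14.2.1.1 are multiple imputation, completers, best case, worst case and all missing as failure. All vary the handling of missing outcomes; none is limited to related events. Neither document describes adjudication of relatedness. SAP 3.2 keeps the words COVID-19 related for time to disease progression, but gives no separate rule for relatedness and presents that analysis as the timing of the primary event. SAP 4.3 restricts SAE summaries to non-COVID events, so it needs a distinction that SAP 3.1 assumes away.

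**Inputs.** Event rates 30% placebo and 15% camostat (Protocol 13.1, SAP 4.1.4); two-sided alpha 0.05 (SAP 4.1.3); 186 + 93 = 279 for 80% power, raised to 200 + 100 (SAP 4.1.4); unadjusted Pearson chi-squared test (SAP 4.1.1). The rate u of unrelated hospitalization or ER visit within 28 days is not in the documents. It is an assumption, taken from 1% to 8%.

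**The plan's own figure.** Exact enumeration of both binomial outcomes at 186/93 with 15% v 30% gives 80.2% for Fisher's test, 78.9% for the continuity-corrected chi-square and 83.0% for Pearson. The stated 80% is reproduced to within 2 points by the first two. Pearson is used below because it is the planned test.

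**Dilution model.** Let unrelated events occur at the same rate u in both arms, independently of treatment and of related events. Then

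p′ = 1 − (1 − p)(1 − u) = p + (1 − p)u,

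and the risk difference is 0.15 × (1 − u).

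Example, u = 5%: placebo 0.30 + 0.70 × 0.05 = 0.335; camostat 0.15 + 0.85 × 0.05 = 0.1925; difference 0.1425 = 0.15 × 0.95; relative risk 0.1925 / 0.335 = 0.57.

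**Power.** Sum the binomial probabilities of all outcomes (x, y) for which |x/n₁ − y/n₂| / √[p̄(1 − p̄)(1/n₁ + 1/n₂)] exceeds 1.96, where p̄ is the pooled proportion.

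| u (assumed) | Placebo | Camostat | Risk difference | Relative risk | Power 200/100 | Power 186/93 |
|---|---|---|---|---|---|---|
| 0 | 30.0% | 15.0% | 15.0 points | 0.50 | 85.3% | 83.0% |
| 1% | 30.7% | 15.9% | 14.9 | 0.52 | 83.7% | 81.3% |
| 2% | 31.4% | 16.7% | 14.7 | 0.53 | 82.1% | 79.5% |
| 3% | 32.1% | 17.6% | 14.6 | 0.55 | 80.5% | 77.7% |
| 5% | 33.5% | 19.3% | 14.3 | 0.57 | 77.1% | 74.0% |
| 8% | 35.6% | 21.8% | 13.8 | 0.61 | 71.9% | 68.6% |

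The pooled normal formula shows the same pattern at 186/93: 82.4% at u = 0 and 73.8% at u = 5%.

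**The case against.** The counting rule has a real rationale. It is applied alike in both blinded arms, the SAP is to be final before unblinding, and it avoids a subjective judgement. Relatedness is hard to judge in patients whose heart, lung or diabetic disease may worsen because of COVID-19. Attribution has its own power cost: if 10% of true events were wrongly called unrelated in both arms (assumed), the rates become 0.30 × 0.90 = 27% and 0.15 × 0.90 = 13.5%, and exact Pearson power at 186/93 falls to 78.0%. That is about the loss from u = 3% (77.7%). SAP 3.1 also states the rule openly and promises a description of the failures, and PP2 may drop confounding intercurrent events.

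Most of this stands, and it means an all-cause primary analysis is a legitimate choice. It does not remove the mismatch between the endpoint named and the endpoint analysed. Neither a narrative description nor a per-protocol set is an ITT analysis of the stated endpoint.

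A reader might also infer four stronger things that the documents do not support:

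- That the trial is underpowered because of the rule. The documents give no value of u, and at 200/100 power stays above 80% up to about 3%.
- That all miscounted events dilute the effect. Hospitalizations caused by the drug would not be equal between arms; they would shift the effect, and the model above does not cover them.
- That the rule inflates type I error. If treatment affects no hospitalization of any kind, the rule is neutral between arms.
- That investigator attribution must be primary. That is a trade-off, as the 78.0% shows. The End of Study form is not shown either, so whether it records cause is unknown.

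**Conclusion.** The inconsistency is certain from the text: SAP 3.1 makes the primary analysis all-cause for hospitalizations and ER visits, while SAP 2.2, 4.1.1 to 4.1.3, the sizing assumption in Protocol 13.1 and the title of shell Table 14.2.1.1 say COVID-19 related. No planned analysis estimates the stated endpoint. Deaths are unaffected, because they are any-cause under both readings.

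The loss of power is conditional. It requires unrelated events at an equal rate in both arms, independent of treatment, and the 30%/15% rates read as Protocol 13.1 words them. At 200/100 the loss is 1.6 points at u = 1% (85.3 − 83.7), 3.2 at 2%, 8.2 at 5% and 13.4 at 8%. If the 30%/15% rates had been meant as all-cause, power would not fall, but the plan would then need to say so. The point should be corrected before database lock; it does not invalidate the design.

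**What to change.** Reconcile SAP 2.2, 3.1, 3.2, 4.1.1 to 4.1.3 and shell Table 14.2.1.1 by one of two routes.

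- Keep the any-cause rule as primary, label the endpoint all-cause hospitalization/ER visit or death throughout, and restate the 30%/15% assumption on that basis.
- Analyse the stated COVID-19 related endpoint as primary, and remove the blanket assumption from SAP 3.1.

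In both cases, add the other version as a named ITT row in Table 14.2.1.1. Classify relatedness blind to treatment, before database lock, from data already collected, and count events of unknown cause as COVID-related. Report how many events were of unknown cause: if most were, the two rows will nearly coincide and should be read that way. Use the same classification for time to progression and for the non-COVID SAE restriction in SAP 4.3.

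The cost is SAP wording and a blinded listing review; SAP 4.7 already sends protocol deviations to sponsor monitors for case review. The downside is some misclassification from judging cause. Source detail may also be thin, since Protocol 12.4.2 says inpatient hospitalization is not treated as an SAE in this study.

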3.2 SECONDARY ANALYSIS (PROTOCOL SPECIFIED)

Time to Resolution of fever (existing at day 0): This analysis will be conducted in the subjects with Day 0 temperature $\geq 100.4^{\circ}\text{F} / 38.0^{\circ}\text{C}$. Time to resolution of fever is defined as the time (in days) from initiation of study treatment (active or placebo) until normalization of fever ($< 100.4^{\circ}\text{F} / 38.0^{\circ}\text{C}$ oral) and sustained for at least 72 hours; this will only be assessed in subjects who experienced a fever within 24 hours of enrollment. In the analysis of time to resolution of fever, temperature is recorded everyday up to day 14. Occurrence of fever is recorded as a binary (yes/no) a fever ($\geq 100.4^{\circ}\text{F} / 38.0^{\circ}\text{C}$) was recorded on the following day using the e-diary.

Time to Disease Progression (Hospitalization/ER visit or Death): Defined as time to disease progression from randomization to either COVID-19 related hospitalization/ER visit or death through Day 28. The primary endpoint is a binary endpoint of Disease Progression, this protocol specified analysis captures the temporal occurrence of the event.

Viral shedding (Resolution): Participants will have Viral Shedding characterized and evaluated as having Viral shedding or not having Viral shedding for this secondary endpoint. Viral shedding will be collected using reverse transcriptase-polymerase chain reaction (RT-PCR) at Day 7, Day 15, and at Day 28 or Early Termination. Subjects will have mid-turbinate nasal samples taken using flocked swabs at onsite study visits. The same nostril should be used for sampling each time it is done, and the nostril (right or left) should be recorded on the eCRF. Use of both nostrils is not to be a Major Protocol Deviation and therefore will have no bearing on the analysis populations. Details of collection method and laboratory requirements are defined in the Clinical Protocol.

3.3 EXPLORATORY ANALYSIS

Time to Resolution of Existing fever (existing by day 3): This analysis will be conducted in the subjects with a fever on Day 0 or those who have a fever within 72 hours of first treatment with fever defined as temperature $\geq 100.4^{\circ}\text{F} / 38.0^{\circ}\text{C}$. Time to resolution of fever is defined as the time (in days) from 72 hours of study treatment (active or placebo) until normalization of fever ($< 100.4^{\circ}\text{F} / 38.0^{\circ}\text{C}$ oral) and sustained for at least 72 hours. In the analysis of time to resolution of fever, temperature is recorded everyday up to day 14.

Time to Incidence of new fever: This analysis will be conducted in the subjects with Day 0 temperature $< 100.4^{\circ}\text{F} / 38.0^{\circ}\text{C}$. Time to incidence of new fever is defined as the time (in days) from initiation of study treatment (active or placebo) until a daily maximum fever $\geq 100.4^{\circ}\text{F} / 38.0^{\circ}\text{C}$ (oral). Daily fever is recorded dichotomously (yes/no) whether a fever of at least $\geq 100.4^{\circ}\text{F} / 38.0^{\circ}\text{C}$ is measured in the e-diary. In the analysis of Time to Incidence of new fever, temperature is recorded everyday up to Day 14.

Time to Resolution of new fever (occurring by Day 11): This analysis will be conducted in the subjects with a new fever defined as temperature $\geq 100.4^{\circ}\text{F} / 38.0^{\circ}\text{C}$ by Day 11. Time to resolution of new fever is defined as the time (in days) from 72 hours of study treatment (active or placebo) until normalization of fever ($< 100.4^{\circ}\text{F} / 38.0^{\circ}\text{C}$ oral) and sustained for at least 72 hours. Occurrence by Day 11 is necessary to capture 72 hours of resolution within the data captured.

Incidence of Fever (any Fever) after Day 0: This analysis will be conducted in the subjects with Day 0 temperature $< 100.4^{\circ}\text{F} / 38.0^{\circ}\text{C}$. New fever is defined as a daily maximum fever $\geq 100.4^{\circ}\text{F} / 38.0^{\circ}\text{C}$ (oral). Daily fever is recorded dichotomously (yes/no) whether a fever of at least $\geq 100.4^{\circ}\text{F} / 38.0^{\circ}\text{C}$ is measured in the e-diary up to Day 14.

Days with Fever: This analysis will be conducted in all subjects in the ITT population through day 14 completing 14 days. For each subject, the occurrence of fever ($\geq 100.4^{\circ}\text{F} / 38.0^{\circ}\text{C}$) will be recorded, 1 for yes, 0 for no. For any missing days of temperature data, the probability of fever on the missing data will be imputed as the mean of the non-missing days. For example, if a subject has 10 (of 14) days of temperature data, and 3 of those days had fever, each of the 4 missing days will be given a value of 0.3. Summary statistics (number of subjects, mean, SD, median, min and max) for the number of days with fever will be characterized. This analysis aims to explore the amount of fever present in time between subjects on IP and not on IP.

Severity of Fever: Shift tables will be provided for the severity of Fever among subjects with a fever at Day 0 using the following classification scheme²:

² The grading for fever was adapted according to FDA categories used in COVID-19 vaccine studies (“U.S. Department of Health and Human Services, Food and Drug Administration, Center for Biologics Evaluation and Research. September 2007. Guidance for Industry. Toxicity Grading Scale for Healthy Adult and Adolescent

- None: < 100.4
- Mild (Grade 1): $\geq 38-38.4^{\circ}\text{C}$ ($\geq 100.4-101.1^{\circ}\text{F}$)
- Moderate (Grade 2): $\geq 38.5-38.9^{\circ}\text{C}$ ($\geq 101.2-102.0^{\circ}\text{F}$)
- Severe (Grade 3): $\geq 39-40^{\circ}\text{C}$ ($\geq 102.1-104.0^{\circ}\text{F}$)
- Potentially Life Threatening (Grade 4): Over 40°C ($\geq 104.0^{\circ}\text{F}$)

A secondary descriptive analysis will be provided in which the status of fever at all points in time will be classified using the among Fever classifications without restricting to Fever at Day 0.

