[figure not shown]
	Number and Percentage with Endpoint						p-value ²	Difference and Confidence Interval (%) ³		
	Camostat mesilate			Placebo				Diff.	LB	UB
Hospitalization/ER visit or death within 28 Days	N	n	%	N	n	%				
Adjusted for baseline covariates with clinically significant group differences ⁴										
Adjusted for all covariates ⁵										
Model identified by stepwise ⁶										

Notes:
 
¹ The Intent-to-Treat (ITT) population will include all subjects who are randomized. Subjects will be analyzed according to their study treatment assignment, not according to the treatment actually received (N=295).
 
² Unadjusted chi-square test
 
³ Two-sided 95% CI
 
⁴ Variable list
 
⁵ Variable list
 
⁶ Variable list
 
Program Source [xxxxxxx.sas]
										

**DRAFT Table 14.2.3
Time to Resolution of Fever
Intent-To-Treat Population**

Interval	Pts at start	#with event	Censored	Cumulative Resolution Rate	SE[‡]
At Start					
Day 1					
...					
Day 14					
Notes: [‡] SE Errors computed using the Peto method. No subjects died on or before Day14. Program source:					

Programming Notes: Time to Resolution of New Fever will be displayed in a similar manner.

**DRAFT Figure 14.2.4
Kaplan-Meier Time to Resolution of Fever
Intent-to-Treat Population**

Program Name: XXXXXX.sas

Database lock date: 17JAN2020; Run Date: 30MAR2021

Note: This figure will include a number At-Risk Table detailing the number of subjects with events and censored for each day of the analysis. Day 0 will be included displaying the number of subjects in the analysis overall.

Programming Notes: Kaplan-Meier Time to COVID-19 Hospitalization/ER visit will be displayed in similar manner.

DRAFT Table 14.2.5
Time to COVID-19 Hospitalization/ER visit or Death
Intent-To-Treat Population

Interval	Pts at start	#with event	Censored	Cumulative Rate	SE[‡]
At Start					
Day 1					
...					
Day 28					

Notes: [‡] SE Errors computed using the Peto method. Program source:
					

**DRAFT Table 14.2.8.1
Shift Table of Fever Severity Categories by Study Day and Treatment**

		Camostat mesilate											Placebo												
		(N=xxx)											(N=xxx)												
		None		Grade 1		Grade 2		Grade 3		Grade 4		Missing		None		Grade 1		Grade 2		Grade 3		Grade 4		Missing	
Study Day		n	%	n	%	n	%	n	%	n	%	n	%	n	%	n	%	n	%			n			%
Day 0	--	xx	xx.x	xx	xx.x	xx	xx.x	xx	xx.x	xx	xx.x	xx	xx.x	xx	xx.x	xx	xx.x	xx	xx.x	xx	xx.x	xx	xx	xx.x	xx.x

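### The exploratory new-fever resolution analysis uses a set formed by fever after dosing, so its arm-by-arm display is not a randomized comparison; two related fever analyses share the problem in a smaller or uncertain degree.

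*SAP*

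**What the plan says.** SAP 3.3 defines three exploratory fever analyses that matter here.

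- **New-fever resolution.** "This analysis will be conducted in the subjects with a new fever defined as temperature" at or above 100.4°F / 38.0°C by Day 11. The only reason given for the cut is data capture: "Occurrence by Day 11 is necessary to capture 72 hours of resolution within the data captured".
- **Resolution of fever existing by day 3.** The set is "subjects with a fever on Day 0 or those who have a fever within 72 hours of first treatment".
- **Days with Fever.** "This analysis will be conducted in all subjects in the ITT population through day 14 completing 14 days". The same paragraph fills missing diary days with the subject's own mean, and gives as its aim a contrast of subjects on and off the investigational product.

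Both resolution clocks start at 72 hours of treatment. The secondary fever endpoint in SAP 3.2 is built differently: "Time to Resolution of fever (existing at day 0): This analysis will be conducted in the subjects with Day 0 temperature" at or above the threshold, with the clock from treatment start. SAP 3.3 also plans time to new fever and incidence of fever in subjects afebrile at Day 0.

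New-fever resolution is missing from the list in SAP 4.5, but the programming note under draft Table 14.2.3 says "Time to Resolution of New Fever will be displayed in a similar manner". SAP 3.3 and 4.5 carry no caveat about sets formed after randomization.

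**The concern.** Randomization makes the arms comparable in sets defined before the first dose. In a set defined by fever after the first dose, they stay comparable only if the drug has no influence on who becomes febrile. Protocol 7.2 hypothesizes that camostat prevents worsening and progression, so that condition cannot be taken for granted.

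A fever that the drug prevents leaves the camostat subset. The remaining question is whether the fevers that were not prevented last equally long, which differs from whether the drug reduces fever. If the prevented fevers are mainly short, those left in the camostat arm are longer on average and the drug appears to slow resolution.

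Days with Fever has a related weakness. Protocol 8.5 allows follow-up after discontinuation to end at hospitalization or death, so completing 14 days can depend on the primary outcome. What is at stake is the reading of the exploratory fever outputs.

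**Working it through.** **1. Plan figures.** The documents give no fever incidence, duration or power, so there is no fever figure to reproduce. The Protocol 13.1 sample size does reproduce (exact Fisher power 80.2% at 183/92), but nothing below depends on it.

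**2. Sets side by side** (Day 0 read as baseline; the protocol calls the first-dose day Day 1).

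| Analysis | Who enters | Fixed before first dose? |
|---|---|---|
| Secondary fever resolution (3.2) | Day 0 febrile | Yes |
| Time to new fever; incidence of fever (3.3) | Day 0 afebrile | Yes |
| Resolution, by day 3 (3.3) | Day 0 febrile, plus febrile within 72 h of dosing | In part |
| Resolution, new fever (3.3) | New fever by Day 11 | No |
| Days with Fever (3.3) | ITT, 14 days completed | No |

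**3. New-fever set: arithmetic.** Assumptions: placebo new-fever risk 35% among Day 0 afebrile subjects; half the fevers short (mean 2 days), half long (mean 5 days).

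- Placebo: mean duration 0.5×2 + 0.5×5 = 3.5 days; fever days per subject 0.35×3.5 = 1.225.
- Drug prevents 50% at random: 0.175×3.5 = 0.6125 fever days per subject. Mean duration among the febrile is still 3.5, so the subset shows nothing.
- Drug prevents 80% of short fevers only: short 0.175×0.2 = 0.035, long 0.175. Fever days per subject 0.035×2 + 0.175×5 = 0.945. Mean duration among the febrile 0.945/0.21 = 4.5 days, one day longer than placebo although the drug lengthened no fever.

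The simulated fever days per subject were 1.21, 0.61 and 0.93, each within 0.02 of these values.

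**4. New-fever set: simulation.** 200:100 subjects, 70% afebrile at Day 0, placebo risk 20%, 35% or 50%, 1,500 runs per scenario, log-rank assumed. A hazard ratio (HR) of resolution above 1 favours the drug.

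- No drug effect: HR 0.99-1.00.
- 50% prevented at random: HR 0.97-1.00, significant benefit in about 2-3% of trials.
- 80% of short fevers prevented: HR 0.71, nominally significant harm in 13-24%. With the clock at fever onset, HR 0.55-0.58 and harm in 24-44%, so selection alone is enough to produce it.

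**5. New-fever set: shortening.** Every fever is cut by one day and one-day fevers vanish (200/100; 40% or 60% new fever; mean duration 3.3-3.5 days). The true change is -1 day per fever. The subset difference depends on the assumed duration law:

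| Duration law | Subset difference (days) |
|---|---|
| Mixed short/long | +0.3 |
| Geometric | 0.0 |
| Negative binomial | -0.4 |
| Poisson | -0.75 |

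The effect is understated in all four.

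**6. By-day-3 set.** Assumptions: Day 0 fever 20% or 40%; new fever within 72 h in 10% or 25% of the rest; mean durations 1.5 and 5 days. The SAP has no rule for a fever that resolves before the 72-hour clock starts, so both readings were run.

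- 80% of short fevers prevented: HR 0.83-0.91 if early resolvers are dropped, 0.93-1.00 if set to time 0.
- Resolution 1.5 times faster: HR 1.45-1.54, against 1.42-1.47 in the Day 0 set. Dropping early resolvers lowers the chance of a significant benefit to 15-22%, from 25-41% when they are kept at time 0.

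**7. Days with Fever.** No drug effect on fever, the SAP's 15%/30% event rates, assumed correlation 0.3-0.7 between severity and event. If every subject with an event leaves the set, camostat looks 0.17-0.40 fever days worse, with nominal rejection in 9-25% of trials. If half leave, the bias is 0.07-0.13 days.

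**The case against.** Several stronger readings are tempting and the documents do not support them.

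- *Both resolution analyses use only subjects who are febrile after dosing.* This is not so for the by-day-3 set: Day 0 fevers enter on baseline status whether or not they persist. It would approach that only if fevers resolved before 72 hours were dropped, which the SAP does not say.
- *A drug that shortens fever will show no effect.* The exact null with geometric durations (5% rejection) is a memoryless property of that law: subtract a day, drop the zeros, and the same law returns. With negative binomial or Poisson durations, a one-day shortening was detected in the benefit direction in 13-85% of trials. In the by-day-3 set a shortening effect stays visible.
- *Invalid tests are planned.* SAP 3.3 and 4.5 name no between-arm test for these analyses. The shell for new-fever resolution has counts, cumulative rate and standard error, with no p-value. The log-rank above is borrowed from SAP 4.2.2. Side-by-side displays still carry the selection.
- *The outputs drive the Phase III decision.* SAP 4.1.6 speaks of the totality of evidence when closing a section on covariate-adjusted primary analyses, and does not name the fever outputs.
- *The all-leave figures for Days with Fever are the expected bias.* They are an upper bound: the 15%/30% rates run to Day 28, so some events come after Day 14, and an emergency room visit need not end diary entry.

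It is also fair that the SAP already plans baseline-defined fever analyses, so a reader would see prevention beside duration. What remains is that the set definitions are as described and no caveat accompanies them.

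**Conclusion.** The point holds for new-fever resolution. Its set is formed entirely after dosing; prevention of fever can appear as no effect, or as harm if short fevers are the ones prevented, and shortening is understated by an amount that depends on the duration law. By day 3, the bias is of the same kind but smaller. For Days with Fever, the completion requirement can introduce outcome-dependent selection of uncertain size.

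All sizes rest on assumed fever incidence, durations and selectivity, because the documents give none; the direction is the finding. The 72-hour clock is a separate matter: a two-day delay in onset with unchanged duration gives HR 0.48-0.49 on that clock but 0.98-1.02 from fever onset.

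Severity is minor. The analyses are exploratory, and the primary endpoint and Day 0 secondary fever endpoint are untouched.

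**What to change.** In SAP 3.3 and 4.5:

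1. State that between-arm fever conclusions rest on baseline-defined sets: incidence of fever and time to new fever in Day 0 afebrile subjects, and fever days to Day 14 in all randomized subjects.
2. Delete the 14-day completion requirement from Days with Fever, and state how diary days after hospitalization or death are counted. Without such a rule, the existing imputation would fill them with the subject's earlier mean.
3. Report new-fever duration, and the post-dose part of the by-day-3 set, as within-arm description only, with a note that the set is defined after randomization. Carry this into the programming note under Table 14.2.3, and list new-fever resolution in 4.5 with that status.

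The cost is SAP wording and reuse of summaries already planned, with no new data. The small loss is that new-fever duration is not available as an arm comparison.

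### The exploratory new-fever resolution clock starts at 72 hours of treatment rather than at fever onset, so late fevers are credited with days before they began

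*SAP*

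**What the plan says.** SAP 3.3 defines two exploratory times to fever resolution with one common origin.

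- **Existing fever (by Day 3).** The set is "subjects with a fever on Day 0 or those who have a fever within 72 hours of first treatment". The clock: "Time to resolution of fever is defined as the time (in days) from 72 hours of study treatment (active or placebo) until normalization". Subjects need not still be febrile at 72 hours.
- **New fever (by Day 11).** The clock: "Time to resolution of new fever is defined as the time (in days) from 72 hours of study treatment (active or placebo) until normalization". Onset has an upper limit but no stated lower limit. The limit is explained by data capture: "Occurrence by Day 11 is necessary to capture 72 hours of resolution within the data captured". It is not tied to the start of the clock.

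Both require normalization sustained for at least 72 hours. Neither says whether the event is dated when the afebrile run begins or when it is confirmed. Follow-up is short: "temperature is recorded everyday up to day 14".

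The 72-hour origin appears only in these two definitions. The secondary fever-resolution endpoint (SAP 3.2) and the exploratory time to new fever (SAP 3.3) both run from initiation of treatment.

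The status of the new-fever analysis is unclear. SAP 4.5 leaves it out of the list of exploratory analyses, and the list of outputs in SAP 5 has no table named for it. A note under draft Table 14.2.3 nevertheless says "Programming Notes: Time to Resolution of New Fever will be displayed in a similar manner".

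**The concern.** A time to resolution should begin when the subject has something to resolve. With a fixed origin and onset on any day up to Day 11, a subject whose fever starts late is counted as at risk of resolution before having a fever. The recorded time then mixes delay to onset with duration. If treatment delayed onset by k days and left duration unchanged, treated subjects would appear to resolve k days later, so a favourable or neutral effect would read as a slower recovery.

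For existing fever the mismatch runs the other way. Some eligible fevers can be over before the clock starts, and the SAP does not say what time such subjects receive.

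**Working it through.** **Inputs.** Clock start is 72 hours, taken as Day 3 to match the SAP's existing-by-Day-3 label. New-fever onset is Day 1 to Day 11, and the last temperature day is Day 14 (SAP 3.3). Confirmation takes three afebrile diary days; this rule is in SAP 4.1.8, written for the secondary endpoint, and I assume it carries over. Each subject is taken to have one continuous episode.

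**The SAP's own figure.** 14 − 3 = Day 11: a fever on Day 11 leaves Days 12, 13 and 14 for confirmation. The Day 11 limit reproduces.

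**New fever.** Let O be the onset day and R the first afebrile day.

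- SAP time = R − 3
- Time from onset = R − O
- Excess = (R − 3) − (R − O) = O − 3

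One-day fevers:

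| Onset O | First afebrile R | SAP time R − 3 | From onset R − O | Excess O − 3 |
|---|---|---|---|---|
| 1 | 2 | −1 | 1 | −2 |
| 3 | 4 | 1 | 1 | 0 |
| 5 | 6 | 3 | 1 | 2 |
| 8 | 9 | 6 | 1 | 5 |
| 11 | 12 | 9 | 1 | 8 |

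Five fevers of equal length get times from −1 to 9 days. For each onset day there are 12 − O possible values of R, so:

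- All patterns, onset Day 1 to 11: 11 + 10 + … + 1 = 66
- Too long, onset Day 4 to 11: 8 + 7 + … + 1 = 36
- Correct, onset Day 3: 9
- Too short, onset Day 1 or 2: 11 + 10 = 21

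Of the 66, 1 has a negative time and 2 have a time of zero.

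**Existing fever.** Onset Day 0 to 3 gives 12 + 11 + 10 + 9 = 42 patterns. The time R − 3 never exceeds time from onset. It is negative in 3 patterns (R = 1 with O = 0; R = 2 with O = 0 or 1) and zero in 3 (R = 3 with O = 0, 1 or 2). A Day 0 fever first normal on Day 1 or Day 2 scores −2 or −1. Against time from treatment start, which is R, every value is shifted by the same 3 days, so the ordering of subjects is unchanged.

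These are counts of possible patterns, not forecasts of patient numbers.

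**Event dated at the third afebrile day.** Both times gain 2 days. The smallest SAP time becomes 1 − 1 = 0 for existing fever and 2 − 1 = 1 for new fever, so no time is negative. The excess is still O − 3: the same 36 of 66 new-fever patterns are too long, by up to 8 days.

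**Day numbering.** The protocol's schedule of assessments sets Study Day 1 as the first dose, which puts 72 hours at Day 4. The Day 11 case becomes 12 − 4 = 8 days against 1, an excess of 7, and the Day 1 case becomes 2 − 4 = −2.

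**The case against.** The strongest reply is that little depends on these definitions. Both analyses are exploratory, and neither SAP 3.3 nor 4.5 specifies a between-group test for them. The secondary fever endpoint has a sound origin, and the Days with Fever summary describes fever burden separately. The new-fever display rests on one note under a draft shell, in a set that the SAP says is subject to revision. All of that stands, and it sets the size of the point. It does not make the definition correct.

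A reader might infer more than the documents support:

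- **That both analyses measure onset instead of duration.** The existing-fever clock is a constant shift from treatment start. Even the new-fever time mixes onset and duration; it does not replace one with the other.
- **That negative times are certain.** They arise only if the event is dated at the first afebrile day. That is the natural reading of a clock running to normalization, but it is not stated.
- **That early resolvers will be dropped by the software.** The documents do not say so. What can be said is that handling is unspecified and the draft table, with rows from the start and Day 1 to Day 14, has no row for a time below zero.
- **That preventing fever would also bias the result in this way.** A subject whose fever is prevented never enters the new-fever set and adds no lengthened time. Only delay has that direct effect.

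**Conclusion.** The new-fever definition is wrong as written. For onset after 72 hours it overstates time to resolution by onset day − 3, up to about 8 days (7 with the first dose as Day 1), under either way of dating the event. The existing-fever definition has a narrower fault: zero or negative times for fevers that resolve by 72 hours, under first-afebrile-day dating, with no rule for them.

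The figures assume one continuous episode and complete diary data. The primary and secondary endpoints and the sample size are unaffected. Even with a corrected clock, the new-fever set is selected on an event after randomization, so it should be read descriptively and not as a randomized comparison.

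**What to change.** In SAP 3.3:

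1. Start the new-fever clock on the first diary day with fever.
2. Start the existing-fever clock at treatment initiation, as SAP 3.2 does, or restrict the set to subjects still febrile at 72 hours so that it is a true landmark analysis. A first-fever-day origin is not workable for fevers already present on Day 0, because the documents describe no variable for when those began.
3. State whether the event is dated at the first or the third afebrile day, and which study day corresponds to 72 hours.
4. Decide whether new-fever resolution is planned, and make SAP 3.3, SAP 4.5 and the note under draft Table 14.2.3 agree.

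The cost is two reworded definitions, a sentence or two on dating, and one list entry or deletion. Daily fever status is already collected, so no new data are needed. The change should be made before unblinding.
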